6.3.1 Outcome variables

Effectiveness outcomes of interest (definitions provided in **Appendix A**):

- Primary outcome: 3-point major adverse cardiovascular events (MACE), i.e., non-fatal myocardial infarction, non-fatal stroke, or CV mortality
- Secondary outcomes: Individual components:
 - o Hospital admission for MI (for purposes of this individual component, fatal MI is included)
 - Hospital admission for stroke (for purposes of this individual component, fatal stroke is included)
 - All-cause mortality/CV mortality:
 - All-cause inpatient mortality identified using discharge status codes will be used as a proxy for "CV mortality" in Marketscan
 - In Optum, all-cause inpatient mortality + all-cause mortality for Medicare Advantage patients is used

Control outcome of interest (control outcome only serve to assess aspects of study validity but are not further interpreted):

- 1. Major bleeding (we expect to see increased risk with prasugrel; Wiviott, 2007)
- 2. Pneumonia (we expect to see a null association)

Control outcome definition

Outcome	Definition	Comments
Control Outcomes		
Major bleeding	Any inpatient diagnosis of major bleeding code list provided in Appendix A	Same code list used for both outcome and major bleed exclusion criteria
Pneumonia	Any inpatient diagnosis of pneumonia: * 481 - PNEUMOCOCCAL PNEUMONIA [STREPTOCOCCUS PNEUMONIAE PNEUMONIA] * 482 - OTHER BACTERIAL PNEUMONIA * 483 - PNEUMONIA DUE TO OTHER SPECIFIED ORGANISM * 485 - BRONCHOPNEUMONIA ORGANISM UNSPECIFIED * 486 - PNEUMONIA ORGANISM UNSPECIFIED * 487.0 - INFLUENZA WITH PNEUMONIA * 507 - PNEUMONITIS DUE TO SOLIDS AND LIQUIDS * 482.0 - PNEUMONIA DUE TO KLEBSIELLA PNEUMONIAE * 482.1 - PNEUMONIA DUE TO PSEUDOMONAS * 482.2 - PNEUMONIA DUE TO PSEUDOMONAS * 482.3 - PNEUMONIA DUE TO STREPTOCOCCUS * 482.3 - PNEUMONIA DUE TO STREPTOCOCCUS GROUP A * 482.3 - PNEUMONIA DUE TO STREPTOCOCCUS GROUP B * 482.3 - PNEUMONIA DUE TO STREPTOCOCCUS GROUP B * 482.3 - PNEUMONIA DUE TO OTHER STREPTOCOCCUS * 482.4 - PNEUMONIA DUE TO STAPHYLOCOCCUS * 482.4 - PNEUMONIA DUE TO STAPHYLOCOCCUS UNSPECIFIED * 482.4 - PNEUMONIA DUE TO STAPHYLOCOCCUS AUREUS * 482.4 - PNEUMONIA DUE TO STAPHYLOCOCCUS BACTERIA * 482.8 - PNEUMONIA DUE TO OTHER SPECIFIED BACTERIA * 482.8 - PNEUMONIA DUE TO OTHER GRAM-NEGATIVE BACTERIA * 482.8 - PNEUMONIA DUE TO OTHER GRAM-NEGATIVE BACTERIA * 482.8 - PNEUMONIA DUE TO OTHER SPECIFIED BACTERIA * 482.8 - PNEUMONIA DUE TO OTHER SPECIFIED BACTERIA * 482.8 - PNEUMONIA DUE TO OTHER SPECIFIED BACTERIA * 482.8 - PNEUMONIA DUE TO OTHER SPECIFIED BACTERIA * 482.8 - PNEUMONIA DUE TO OTHER SPECIFIED BACTERIA * 482.9 - BACTERIAL PNEUMONIA UNSPECIFIED * 483.1 - PNEUMONIA DUE TO OTHER SPECIFIED BACTERIA	and major bleed exclusion criteria PPV = 85% (Aronsky, et al.; 2005); Note- The corresponding ICD-10 codes will also be used

* 507.0 - PNEUMONITIS DUE TO INHALATION OF FOOD OR VOMITUS	
* 507.1 - PNEUMONITIS DUE TO INHALATION OF OILS AND ESSENCES	
* 507.8 - PNEUMONITIS DUE TO OTHER SOLIDS AND LIQUIDS	

6.3.2 Study follow-up

Both as-treated (AT) and intention-to-treat (ITT) analyses will be conducted with treatment defined as the index drug on the day of cohort entry. Because adherence in the real-world databases is expected to be much worse than in the trial, the AT analysis is the **primary** analysis, as it targets the relative hazard of outcomes on treatment.

For the AT analyses, the follow-up will start the day after initiation of prasugrel and comparator and will continue until the earliest date of the following events:

- The first occurrence of the outcome of interest, unless otherwise specified for selected outcomes,
- The date of end of continuous registration in the database,
- End of the study period,
- Measured death event occurs,
- Nursing home admission
 - Nursing home admissions are considered a censoring event because the data sources utilized typically provide little to no data on a patient, particularly on drug utilization, after admission. We will utilize this as an exclusion reason for cohorts for the same reason.
- The date of drug discontinuation, defined as the date of the last continuous treatment episode of the index drug (prasugrel and comparator) plus a defined grace period (i.e., 30 days after the end of the last prescription's days' supply in main analyses).
- The date of augmentation or switching from an exposure to a comparator
- Initiation of ticagrelor

For the ITT analyses, the censoring based on the augmentation/switching and treatment discontinuation will be replaced with a maximum allowed follow-up time of 365 days.

7. Initial Feasibility Analysis

Aetion report links:

Optum: https://bwh-dope.aetion.com/projects/details/989/results/46156/result/0 Marketscan: https://bwh-dope.aetion.com/projects/details/990/results/46157/result/0

Date conducted: December 15, 2019

Complete Aetion feasibility analysis using age, sex, and CCI as the only covariates and the primary endpoint (Section 6.3.1) as the outcome. No measures of association will be computed nor will incidence rates stratified by treatment group.

- Report patient characteristics by treatment group
- Report summary parameters of the overall study population
- Report median follow-up time by treatment group
- Report reasons for censoring in the overall study population

8. Initial Power Assessment

Aetion report links:

Optum: https://bwh-dope.aetion.com/projects/details/989/results/46159/result/0
Marketscan: https://bwh-dope.aetion.com/projects/details/990/results/46158/result/0

Date conducted: December 15, 2019

In order to complete the initial power analysis, the dummy outcome of a 90-day gap in database enrollment will be used. This outcome is used to ensure that no information on the comparative risks of the outcomes of interest are available at this stage. Complete a 1:1 PS-matched comparative analysis using this outcome. PS should include only 3 covariates: age, sex, and combined comorbidity index. Power calculations are based on the formulas from Chow et al. (2008).

In order to complete the initial power analysis, the dummy outcome of a 90-day gap in database enrollment will be used. This outcome is used to ensure that no information on the comparative risks of the outcomes of interest are available at this stage.

Effectiveness research with Real World Data to support FDA's regulatory decision making: Protocol Template

Complete a 1:1 PS-matched comparative analysis using this outcome. PS should include only 3 covariates: age, sex, and combined comorbidity index. Power calculations are based on the formulas from Chow et al. (2008).

Reviewed by PI:	[name]	Date reviewed:	12/16/19
Reviewed by FDA:	[name]	Date reviewed:	1/2/20
Reasons for stopping			
analysis (if required):			

9. Balance Assessment after PS matching

Aetion report links (Prasugrel vs. clopidogrel):

Optum: https://bwh-dope.aetion.com/projects/details/989/results/46940/result/0
Marketscan: https://bwh-dope.aetion.com/projects/details/990/results/46941/result/0

Date conducted: 01/05/2020

After review of initial feasibility and power analyses, complete creation of the remaining covariates (see Table 1 below for list of covariates). Again, using the dummy outcome of a 90-day gap in database enrollment, complete a 1:1 PS-matched analysis. The PS should include the complete list of covariates (excluding laboratory values, which are missing in some patients).

• Provide plot of PS distributions stratified by treatment group.

Note- Please refer to Appendix B.

Report covariate balance after matching.

Note- For Table 1, please refer to Appendix B.

• Report reasons for censoring by treatment group.

  		
Overall	Referent	Exposure

Effectiveness research with Real World Data to support FDA's regulatory decision making

Dummy Outcome	0 (0.00%)	0 (0.00%)	0 (0.00%)
Death	123 (0.28%)	70 (0.32%)	53 (0.24%)
Start of an additional exposure	3,840 (8.75%)	580 (2.64%)	3,260 (14.86%)
End of index exposure	22,870 (52.14%)	11,391 (51.94%)	11,479 (52.34%)
Specified date reached	3,735 (8.51%)	2,262 (10.31%)	1,473 (6.72%)
End of patient enrollment	12,361 (28.18%)	7,033 (32.07%)	5,328 (24.29%)
Switch to ticagrelor (for censoring) + nursing home admission	935 (2.13%)	596 (2.72%)	339 (1.55%)

• Report follow-up time by treatment group.

Median Follow-Up Time (Days) [IQR]				
Patient Group Optum Marketscan				
Overall Patient Population	276 [98-453]	312 [122-481]		
Referent	332 [124-532]	344 [144-530]		
Exposure	222 [82-405]	281 [111-443]		

• Report overall risk of the primary outcome.

	Optum	Marketscan
Risk per 1,000 patients (MACE)	58.63	45.09

10. Final Power Assessment

Date conducted:

- Re-calculate power in the appropriate excel table, using the revised number of matched patients from the PS-match in Section 9. All other parameters in the table should be the same as in Section 8. If the study is to be implemented in more than one database, copy and paste excel sheet to report power for each database separately and for the pooled analysis that uses data from all databases together. Power calculations are based on the formulas from Chow et al. (2008).
 - Pooled
 - For prasugrel 10mg vs. clopidogrel 75mg (Primary outcome- MACE)

Superiority Analysis		Non-inferiority Analysis	
Number of patients matched		Number of patients matched	
Reference	21,932	Reference	21,932
Exposed	21,932	Exposed	21,932
Risk per 1,000 patients	51.86	Risk per 1,000 patients	51.86
Desired HR from RCT	0.8	Assumed HR from RCT	1
Alpha (2-sided)	0.05	Alpha (2-sided)	0.05
		Non-inferiority margin	1.3
Number of events expected	2274.78704	Number of events expected	2274.78704
Power	0.999612288	Power	0.999991333

o Optum

For prasugrel 10mg vs. clopidogrel 75mg (Primary outcome- MACE)

Superiority Analysis		Non-inferiority Analysis	
Number of patients matched		Number of patients matched	
Reference	6,835	Reference	6,835
Exposed	6,835	Exposed	6,835
Risk per 1,000 patients	58.63	Risk per 1,000 patients	58.63
Desired HR from RCT	0.8	Assumed HR from RCT	1
Alpha (2-sided)	0.05	Alpha (2-sided)	0.05
		Non-inferiority margin	1.3
Number of events expected	801.4721	Number of events expected	801.4721
Power	0.884670943	Power	0.960270972

MarketScan

For prasugrel 10mg vs. clopidogrel 75mg (Primary outcome- MACE)

Tot prasagret total vs. clopidogret 75 mg (1 milar y outcome-winee)			
Superiority Analysis		Non-inferiority Analysis	
Number of patients matched		Number of patients matched	
Reference	15,097	Reference	15,097
Exposed	15,097	Exposed	15,097
Risk per 1,000 patients	45.09	Risk per 1,000 patients	45.09
Desired HR from RCT	0.8	Assumed HR from RCT	1
Alpha (2-sided)	0.05	Alpha (2-sided)	0.05
		Non-inferiority margin	1.3
Number of events expected	1361.44746	Number of events expected	1361.44746
Power	0.984488939	Power	0.998013942

• Stop analyses until balance and final power assessment are reviewed by primary investigators, FDA, and assigned members of advisory board. Reviewers evaluate the results of the analyses described above in Sections 9 and 10, including numbers of patients, balance in patient characteristics, follow-up time, and reasons for censoring by treatment group, as well as overall rates of outcomes and study power.

Reviewed by PI:	[name]	Date reviewed:	12/16/19
Reviewed by FDA:	[name]	Date reviewed:	01/02/2020
Reasons for stopping			
analysis (if required):			

11. Study Confidence and Concerns

Deadline for voting on study confidence and listing concerns: 1/10/20

- If final feasibility and power analyses are reviewed and approved, proceed to the remaining protocol steps.
- All study team and advisory board members that review this protocol should at this stage provide their level of confidence for the
 success of the RWD study in the Google Form. This form also provides space for reviewers to list any concerns that they feel may
 contribute to a failure to replicate the findings of the RCT, including differences in study populations, poor measurement of study
 variables, or residual confounding. All responses will be kept confidential and individual-level results will only be shared with the
 individual respondent.

12. Register study protocol on clinicalTrials.gov

Date conducted:

• Register the study on clinicalTrials.gov and upload this document.

13. Comparative Analyses

Aetion report name:

Date conducted:

13.1 For primary analysis:

• In the PS-matched cohort from Section 9, calculate the HR for each outcome for prasugrel versus clopidogrel patients using a Cox proportional hazards model.

13.2 For secondary analyses:

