Final cohort		39,448		66,003

6. Variables

6.1 Exposure-related variables:

Study drug:

The study exposure of interest is initiation of Prasugrel. Initiation will be defined by no use of Prasugrel or a comparator in the prior 6 months before treatment initiation (washout period).

Effectiveness research with Real World Data to support FDA's regulatory decision making: Protocol Template

Comparator agents:

- Initiators of prasugrel 10mg will be compared to initiators of-
 - Clopidogrel 75mg

6.2 Preliminary covariates:

- Age
- Sex
- Combined Comorbidity Index (CCI), measured over the default baseline covariate assessment period, defined as 180 days prior to and including index date

Covariates listed above represent only a small subset of covariates that will ultimately be controlled for in the design and analysis. We use the covariates above only for initial feasibility analyses to judge whether there is likely to be sufficient overlap between treatment groups to proceed with the study. Remaining covariates are defined only after the study has passed the initial feasibility analysis and the initial power assessment and are listed in Table 1 (Appendix B).

6.3 Outcome variables and study follow-up:

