median [IQR]	0.00 [0.00, 0.00]	0.00 [0.00, 0.00]	0.00	0.00 [0.00, 0.00]	0.00 [0.00, 0.00]	0.00	0.00 (0.02)	0.00 (0.01)	0.00
HAS-BLED Score (ICD-9 and ICD-10), 180							,	,	
days									
mean (sd)	3.74 (0.76)	3.42 (0.67)	0.45	3.38 (0.65)	3.16 (0.50)	0.38	3.52 (0.70)	3.24 (0.56)	0.44
median [IQR]	4.00 [3.00, 4.00]	3.00 [3.00, 4.00]	1.40	3.00 [3.00, 4.00]	3.00 [3.00, 3.00]	0.00	3.39 (0.70)	3.00 (0.56)	0.62
Drug eluting stent; n (%)	14,767 (45.4%)	3,976 (57.9%)	-0.25	21,794 (42.9%)	7,216 (47.5%)	-0.09	36,561 (43.9%)	11192 (50.7%)	-0.14
Bare metal stent; n (%)	21,714 (66.7%)	4,304 (62.6%)	0.09	23,619 (46.5%)	7,240 (47.7%)	-0.02	45,333 (54.4%)	11544 (52.3%)	0.04
Use of CYP inhibitors; n (%)	5,868 (18.0%)	1,035 (15.1%)	0.08	8,155 (16.1%)	2,209 (14.5%)	0.04	14,023 (16.8%)	3244 (14.7%)	0.06
Use of CYP inducers; n (%)	237 (0.7%)	32 (0.5%)	0.03	363 (0.7%)	83 (0.5%)	0.03	0,600 (0.7%)	115 (0.5%)	0.03
Commercial vs Medicare Advantage-	- (,	(- ()		,	,		-, (,	- (/	
Business Type Code - CORRECT ONE -									
TRUVEN									
Commercial; n (%)	14,856 (45.6%)	4,721 (68.7%)	-0.48	15,837 (31.2%)	2,186 (14.4%)	0.41	30,693 (36.8%)	6907 (31.3%)	0.12
Medicare Advantage; n (%)	17,700 (54.4%)	2,151 (31.3%)	0.48	34,958 (68.8%)	13,001 (85.6%)	-0.41	52,658 (63.2%)	15152 (68.7%)	-0.12
Commercial vs Medicare Advantage-									
Business Type Code	14.056 (45.60/)	4 724 (60 70/)	0.40			40.401.1151	14 056 (45 60/)	4 724 (60 70/)	0.40
COM = COMMERCIAL; n (%)	14,856 (45.6%)	4,721 (68.7%)	-0.48	-	-	#VALUE!	14,856 (45.6%)	4,721 (68.7%)	-0.48
MCR = MEDICARE; n (%)	17,700 (54.4%)	2,151 (31.3%)	0.48	-	-	#VALUE!	17,700 (54.4%)	2,151 (31.3%)	0.48
MCD = MEDICAID; n (%)	0 (0.0%)	0 (0.0%)	#DIV/0!	-	-	#VALUE!	0 (0.0%)	0 (0.0%)	#DIV/0!
NONE = NO BUSINESS LINE CODE (added	0 (0.0%)	0 (0.0%)	#DIV/0!	-	-	#VALUE!	0 (0.0%)	0 (0.0%)	#DIV/0!
in 2015); n (%) UNK = UNKNOWN (added in 2015); n (%)	0 (0.0%)	0 (0.0%)	#DIV/0!	-	-	#VALUE!	0 (0.0%)	0 (0.0%)	#DIV/0!
Commercial vs Medicare Advantage- Data									
Type 1 - Fee For Service; n (%)			#VALUE!	30,527 (60.1%)	11,547 (76.0%)	-0.35	30,527 (60.1%)	11,547 (76.0%)	-0.35
' ' '	-	-	#VALUE!			-0.35 -0.03			-0.35 -0.03
2 - Encounter; n (%)	-	-	#VALUE!	4,431 (8.7%) 13,608 (26.8%)	1,454 (9.6%)	-0.03 0.36	4,431 (8.7%)	1,454 (9.6%)	-0.03 0.36
3 - Medicare; n (%) 4 - Medicare Encounter; n (%)	-	-	#VALUE!	2,229 (4.4%)	1,922 (12.7%) 264 (1.7%)	0.36	13,608 (26.8%) 2,229 (4.4%)	1,922 (12.7%) 264 (1.7%)	0.36

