Use of digoxin- United; n (%)	58 (0.8%)	49 (0.7%)	0.01	95 (0.6%)	94 (0.6%)	0.00	153 (0.7%)	143 (0.7%)	0.00
Use of Anti-arrhythmics; n (%)	84 (1.2%)	88 (1.3%)	-0.01	178 (1.2%)	170 (1.1%)	0.01	262 (1.2%)	258 (1.2%)	0.00
Use of COPD/asthma meds- United; n (%)	737 (10.8%)	744 (10.9%)	0.00	1,626 (10.8%)	1,640 (10.9%)	0.00	2,363 (10.8%)	2,384 (10.9%)	0.00
Use of statins; n (%)	6,235 (91.2%)	6,239 (91.3%)	0.00	13,750 (91.1%)	13,729 (90.9%)	0.01	19,985 (91.1%)	19,968 (91.0%)	0.00
Use of other lipid-lowering drugs; n (%)	578 (8.5%)	598 (8.7%)	-0.01	1,382 (9.2%)	1,425 (9.4%)	-0.01	1,960 (8.9%)	2,023 (9.2%)	-0.01
Use of oral anticoagulants (Dabigatran, Rivaroxaban, Apixaban, Warfarin); n (%)	167 (2.4%)	171 (2.5%)	-0.01	405 (2.7%)	393 (2.6%)	0.01	0,572 (2.6%)	0,564 (2.6%)	0.00
Use of heparin and other low-molecular weight heparins; n (%)	31 (0.5%)	29 (0.4%)	0.01	2 (0.0%)	2 (0.0%)	#DIV/0!	33 (0.2%)	31 (0.1%)	0.03
Use of NSAIDs; n (%)	868 (12.7%)	891 (13.0%)	-0.01	1,920 (12.7%)	1,952 (12.9%)	-0.01	2,788 (12.7%)	2,843 (13.0%)	-0.01
Use of oral corticosteroids; n (%)	936 (13.7%)	946 (13.8%)	0.00	1,934 (12.8%)	2,015 (13.3%)	-0.01	2,870 (13.1%)	2,961 (13.5%)	-0.01
Use of bisphosphonate (United); n (%)	45 (0.7%)	58 (0.8%)	-0.01	72 (0.5%)	82 (0.5%)	0.00	117 (0.5%)	140 (0.6%)	-0.01
Use of opioids- United; n (%)	1,585 (23.2%)	1,555 (22.8%)	0.01	3,186 (21.1%)	3,248 (21.5%)	-0.01	4,771 (21.8%)	4,803 (21.9%)	0.00
Use of antidepressants; n (%)	1,047 (15.3%)	1,049 (15.3%)	0.00	2,039 (13.5%)	2,076 (13.8%)	-0.01	3,086 (14.1%)	3,125 (14.2%)	0.00
Use of antipsychotics; n (%)	45 (0.7%)	44 (0.6%)	0.01	104 (0.7%)	107 (0.7%)	0.00	0,149 (0.7%)	0,151 (0.7%)	0.00
Use of anticonvulsants; n (%)	503 (7.4%)	494 (7.2%)	0.01	775 (5.1%)	783 (5.2%)	0.00	1,278 (5.8%)	1,277 (5.8%)	0.00
Use of lithium- United; n (%)	9 (0.1%)	7 (0.1%)	0.00	16 (0.1%)	17 (0.1%)	0.00	25 (0.1%)	24 (0.1%)	0.00
Use of Benzos- United; n (%)	646 (9.5%)	660 (9.7%)	-0.01	1,460 (9.7%)	1,411 (9.3%)	0.01	2,106 (9.6%)	2,071 (9.4%)	0.01
Use of anxiolytics/hypnotics- United; n (%)	334 (4.9%)	351 (5.1%)	-0.01	798 (5.3%)	809 (5.4%)	0.00	1,132 (5.2%)	1,160 (5.3%)	0.00
Use of dementia meds- United; n (%)	14 (0.2%)	14 (0.2%)	0.00	15 (0.1%)	13 (0.1%)	0.00	29 (0.1%)	27 (0.1%)	0.00
Use of antiparkinsonian meds- United; n (%)	60 (0.9%)	63 (0.9%)	0.00	122 (0.8%)	118 (0.8%)	0.00	0,182 (0.8%)	0,181 (0.8%)	0.00
Entresto (sacubitril/valsartan); n (%) Labs	1 (0.0%)	2 (0.0%)	#DIV/0!	1 (0.0%)	2 (0.0%)	#DIV/0!	2 (0.0%)	4 (0.0%)	#DIV/0!

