median [IQR]	0.00 [0.00, 0.00]	0.00 [0.00, 0.00]	0.00	0.00 [0.00, 0.00]	0.00 [0.00, 0.00]	0.00	0.00 (0.01)	0.00 (0.01)	0.00
HAS-BLED Score (ICD-9 and ICD-10),									
180 days									
mean (sd)	3.41 (0.67)	3.42 (0.67)	-0.01	3.16 (0.49)	3.16 (0.50)	0.00	3.24 (0.55)	3.24 (0.56)	0.00
median [IQR]	3.00 [3.00, 4.00]	3.00 [3.00, 4.00]	0.00	3.00 [3.00, 3.00]	3.00 [3.00, 3.00]	0.00	3.00 (0.55)	3.00 (0.56)	0.00
Drug eluting stent; n (%)	3,921 (57.4%)	3,947 (57.7%)	-0.01	7,223 (47.8%)	7,159 (47.4%)	0.01	11,144 (50.8%)	11106 (50.6%)	0.00
Bare metal stent; n (%)	4,286 (62.7%)	4,285 (62.7%)	0.00	7,177 (47.5%)	7,200 (47.7%)	0.00	11,463 (52.3%)	11485 (52.4%)	0.00
Use of CYP inhibitors; n (%)	1,028 (15.0%)	1,027 (15.0%)	0.00	2,162 (14.3%)	2,184 (14.5%)	-0.01	3,190 (14.5%)	3211 (14.6%)	0.00
Use of CYP inducers; n (%)	27 (0.4%)	32 (0.5%)	-0.01	94 (0.6%)	83 (0.5%)	0.01	0,121 (0.6%)	115 (0.5%)	0.01
Commercial vs Medicare Advantage-									
Business Type Code - CORRECT ONE -									
TRUVEN									
Commercial; n (%)	4,740 (69.3%)	4,686 (68.6%)	0.02	2,090 (13.8%)	2,184 (14.5%)	-0.02	6,830 (31.1%)	6870 (31.3%)	0.00
Medicare Advantage; n (%)	2,095 (30.7%)	2,149 (31.4%)	-0.02	13,007 (86.2%)	12,913 (85.5%)	0.02	15,102 (68.9%)	15062 (68.7%)	0.00
Commercial vs Medicare Advantage-									
Business Type Code									
COM = COMMERCIAL; n (%)	4,740 (69.3%)	4,686 (68.6%)	0.02	-	-	#VALUE!	4,740 (69.3%)	4,686 (68.6%)	0.02
MCR = MEDICARE; n (%)	2,095 (30.7%)	2,149 (31.4%)	-0.02	-	-	#VALUE!	2,095 (30.7%)	2,149 (31.4%)	-0.02
MCD = MEDICAID; n (%)	0 (0.0%)	0 (0.0%)	#DIV/0!	-	-	#VALUE!	0 (0.0%)	0 (0.0%)	#DIV/0!
NONE = NO BUSINESS LINE CODE	0 (0.0%)	0 (0.0%)	#DIV/0!	-	-	#VALUE!	0 (0.0%)	0 (0.0%)	#DIV/0!
(added in 2015); n (%)									
UNK = UNKNOWN (added in 2015); n	0 (0.0%)	0 (0.0%)	#DIV/0!	-	-	#VALUE!	0 (0.0%)	0 (0.0%)	#DIV/0!
(%)									
Commercial vs Medicare Advantage-									
Data Type									
1 - Fee For Service; n (%)	-	-	#VALUE!	11,534 (76.4%)	11,465 (75.9%)	0.01	11,534 (76.4%)	11,465 (75.9%)	0.01
2 - Encounter; n (%)	-	-	#VALUE!	1,473 (9.8%)	1,448 (9.6%)	0.01	1,473 (9.8%)	1,448 (9.6%)	0.01
3 - Medicare; n (%)	-	-	#VALUE!	1,821 (12.1%)	1,920 (12.7%)	-0.02	1,821 (12.1%)	1,920 (12.7%)	-0.02
4 - Medicare Encounter; n (%)	-	-	#VALUE!	269 (1.8%)	264 (1.7%)	0.01	269 (1.8%)	264 (1.7%)	0.01
Metropolitan Statistical Area - Urban									
(any MSA) vs Rural (non-MSA)									
Urban; n (%)	-	-	#VALUE!	11,804 (78.2%)	11,827 (78.3%)	0.00	11,804 (78.2%)	11,827 (78.3%)	0.00

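### Table 1 has no row for acid-suppressing drugs or non-bleeding ulcer/reflux disease, so they are not explicitly in the propensity score and their balance is not reported

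*Combined protocol and SAP*

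**What the plan says.** Section 6.2 starts from age, sex and the comorbidity index, and says the remaining covariates "are listed in Table 1 (Appendix B"). Section 9 then asks the analyst to "complete creation of the remaining covariates (see Table 1 below for list of covariates") and fixes the propensity score (PS): "The PS should include the complete list of covariates (excluding laboratory values, which are missing in some patients"). Table 1 is therefore the PS specification.

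Table 1 has roughly 45 drug rows. On drug metabolism there are two: "Use of CYP inhibitors; n" and "Use of CYP inducers; n". Neither lists its member drugs. On bleeding risk it has "HAS-BLED Score (ICD-9 and ICD-10"), "Use of NSAIDs; n", oral corticosteroids and oral anticoagulants. It has no row for proton-pump inhibitors (PPIs), H2 blockers, reflux disease or non-bleeding peptic ulcer.

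Section 6.3.1 makes major bleeding a control outcome with a stated direction: "we expect to see increased risk with prasugrel". It serves only to assess validity. The same code list drives the baseline bleeding exclusion.

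**The concern.** In a study that compares two antiplatelet drugs and checks itself against bleeding, a marker of perceived gastrointestinal risk should be visible in the covariate table. If prescribers who worry about gastrointestinal bleeding both favour one drug and add acid suppression, the marker is linked to treatment and to the bleeding control, and possibly to MACE. The present table cannot show whether the matched arms differ on it.

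The main stake is how to read the control. A bleeding hazard ratio above 1 is meant to reassure the reader that the design recovers a known effect. A gastrointestinal-risk marker of unknown balance makes that reading less secure. The stake for the primary MACE hazard ratio is smaller.

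**Working it through.** **1. Is the omission real?** Both halves of Table 1 (unmatched and PS-matched) were read through. No row names PPIs, H2 blockers, reflux or non-bleeding ulcer, and the terms do not appear elsewhere in the text. The bleeding exclusion (Appendix A, criterion 6 and the bleeding code sheet) lists gastric, duodenal, peptic and gastrojejunal ulcer only with haemorrhage. Non-bleeding ulcer and reflux are therefore neither excluded by it nor tabulated.

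**2. Does treatment choice track bleeding risk before matching?** The inputs are the pooled unmatched columns. The pooled exposure column is headed ticagrelor, but its N is 6,872 + 15,187 = 22,059, the prasugrel total.
- HAS-BLED, clopidogrel 3.52 (SD 0.70) vs prasugrel 3.24 (SD 0.56): (3.52 − 3.24)/√((0.70² + 0.56²)/2) = 0.28/0.634 = 0.44. Table 1 gives 0.44.
- Oral anticoagulants, 5,948/83,351 = 7.1% vs 564/22,059 = 2.6%: with SMD = (p0 − p1)/√((p0(1−p0) + p1(1−p1))/2), 0.0458/0.2135 = 0.21. Table 1 gives 0.21.

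So it does, and clopidogrel goes to the higher-risk patients.

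**3. What do the existing rows show after matching (pooled)?**
- CYP inhibitors: 3,190/21,932 = 14.5% vs 3,211/21,932 = 14.6%, SMD −0.003 (unmatched 16.8% vs 14.7%, SMD 0.058).
- HAS-BLED 3.24 vs 3.24; NSAIDs 12.7% vs 13.0%; oral corticosteroids 13.1% vs 13.5%; anticoagulants 2.6% vs 2.6%. Every absolute standardised difference is at most 0.01.

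Balance on one summary does not settle balance on a finer feature. Pooled mean age matches (−0.02), yet age 75 and over is 6.6% vs 3.1% (0.16) after matching.

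**4. How much of the bleeding control is gastrointestinal?** A hand count of the diagnosis rows gives about 97 gastrointestinal or intraperitoneal and about 104 other (intracranial, joint, respiratory, urinary, pericardial, unspecified). 97/201 = 48%. This is a share of code rows, not of events.

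**5. How large could the effect be?** The documents give neither PPI prevalence by arm nor any association with outcome. Everything here is assumed: 20% use in one matched arm (p0), 22%, 25% or 30% in the other (p1), RR 1.3 for MACE and 1.5 for bleeding. Bias factor = (1 + p1(RR − 1))/(1 + p0(RR − 1)).

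| Gap | MACE (RR 1.3) | 0.81 would read | Bleeding (RR 1.5) |
|---|---|---|---|
| 0 | 1.000 | 0.81 | 1.000 |
| 2 points | 1.066/1.060 = 1.006 | 0.805 or 0.815 | 1.110/1.100 = 1.009 |
| 5 points | 1.075/1.060 = 1.014 | 0.799 or 0.821 | 1.125/1.100 = 1.023 |
| 10 points | 1.090/1.060 = 1.028 | 0.788 or 0.833 | 1.150/1.100 = 1.045 |

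The two readings of 0.81 correspond to the two directions of imbalance. With RR 2.0 and a 5-point gap the factor is 1.25/1.20 = 1.042.

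**6. Against sampling error.** The pooled power table's events reproduce: 2 × 21,932 × 51.86/1000 = 2,274.8. SE(log HR) ≈ 2/√2,274.8 = 0.042, so the 95% interval is about ±8%. The MACE shifts above are 0.006 to 0.028 on the log scale, or about 0.13 to 0.67 of a standard error. Power and sample size are not affected by this point.

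**The case against.** The other side has several good arguments, and most of them limit the point.

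- *The CYP-inhibitor row may already cover it.* Its drugs are not listed, and Appendix A refers to an external folder for missing detail. A reader might infer that PPI use is wholly unadjusted; the documents do not establish that. Equally, balance on an unnamed mix of drugs does not show balance on PPIs.
- *The bleeding pathway is largely handled.* HAS-BLED, NSAIDs, steroids and anticoagulants are balanced, and the baseline exclusion is aimed at recent bleeding, including bleeding ulcers. This stands and lowers the likely residual. None of these rows records acid suppression or non-bleeding disease.
- *The drug-interaction argument.* A reader might infer that PPIs confound the comparison because they could weaken clopidogrel's activation. The documents say nothing of this mechanism. Taken alone, it would be effect modification within the clopidogrel arm. Confounding also needs use to differ between the matched arms, and no evidence of that is given.
- *The sizes are assumed.* Gaps of 5 to 10 points are well above the 2.1-point crude gap for CYP inhibitors (16.8% − 14.7%), and the matched gap there is 0.1 point. The 2-point row is the closest to anything observed. This stands: the table is a sensitivity range, not an estimate of bias.
- *The Section 9 sentence is not wrong.* Agreed. The gap is in the list it points to.

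**Conclusion.** The point holds in a limited form. Acid suppression and non-bleeding reflux/ulcer disease are not named in the list that defines the PS, and their balance is not reported. Acid suppression is a plausible residual confounder, mainly of the bleeding control, because allocation tracked bleeding risk before matching and about half of that control's code rows are gastrointestinal. That it marks gastrointestinal risk is an assumption the documents do not test.

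The size is small: about 0.6% to 3% on the MACE hazard ratio for an assumed gap of 2 to 10 points and RR 1.3, and about 0.9% to 4.5% on bleeding at RR 1.5, in either direction. It is zero if the matched arms do not differ. The documents do not show that the result is biased. This is an inexpensive improvement, not a flaw that threatens the study.

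**What to change.** Before the Section 13 analyses (their date is still blank):

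1. Add to the Section 9 PS, measured in the 180-day baseline: any PPI fill, any H2-blocker fill, and a reflux or non-bleeding peptic ulcer diagnosis.
2. Re-run the match in each database and show these rows in both halves of Table 1.
3. State which drugs make up the CYP-inhibitor row. If PPIs are already counted there, say so, and still tabulate them separately so that their balance can be seen.

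The cost is a few covariate definitions, one re-run and possibly a few fewer matched pairs. Over-the-counter use stays unmeasured and should be stated as a limitation.

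### Section 10's pooled power table averages the two database risks without weighting, so its expected event count exceeds the sum of the database tables by 112 (5.2%)

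*Combined protocol and SAP*

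**What the plan says.** Section 9 reports the overall risk of the primary outcome in each database, Optum first and MarketScan second: "Risk per 1,000 patients (MACE) 58.63 45.09".

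Section 10 then gives three power tables, each with a superiority and a non-inferiority column:

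- Pooled: "Reference 21,932" and the same number exposed, "Risk per 1,000 patients 51.86", "Number of events expected 2274.78704".
- Optum: "Reference 6,835" and the same number exposed, risk 58.63 per 1,000, 801.4721 events.
- MarketScan: "Reference 15,097" and the same number exposed, risk 45.09 per 1,000, 1361.44746 events.

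The pooled table is meant to describe an analysis of both databases combined; the instruction is to "report power for each database separately and for the pooled analysis that uses data from all databases together". All three tables use a two-sided alpha of 0.05. The superiority columns enter 0.8 on the row labelled "Desired HR from RCT". The non-inferiority columns assume a true hazard ratio of 1 against a margin of 1.3.

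Section 1.5 names HR 0.81 (95% CI 0.73 to 0.90) as the estimate to replicate. Section 1.4 gives the randomised trial's own design effect as a 20% relative reduction.

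**The concern.** The pooled arms are exactly the two databases' arms added together (6,835 + 15,097 = 21,932). The pooled expected events should therefore equal the sum of the two database counts, and they do not. The pooled risk lies midway between the two database risks, whereas a patient-weighted risk would lie closer to MarketScan's lower figure.

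Section 10 halts the analyses until the investigators, FDA and advisory board members have looked at the outcome rates and the power, and Section 12 has the document uploaded to a public registry. Those readers are given a pooled outcome rate and event count that the adjoining tables contradict.

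**Working it through.** **Inputs.** Risks per 1,000: 58.63 (Optum) and 45.09 (MarketScan), from Section 9. Matched patients per arm: 6,835, 15,097 and 21,932, from Section 10. Alpha 0.05 two-sided, HR 0.80 for superiority, margin 1.3 with true HR 1 for non-inferiority, 1:1 matching.

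**Step 1: reproduce the plan's figures.** Expected events D = 2 × patients per arm × risk / 1,000.

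- Pooled: 2 × 21,932 × 0.05186 = 2,274.787
- Optum: 2 × 6,835 × 0.05863 = 801.472
- MarketScan: 2 × 15,097 × 0.04509 = 1,361.447

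Superiority power = Φ(√(D/4) × |ln HR| − 1.96). Non-inferiority power is the same expression with ln 1.3 in place of |ln HR|. These reproduce all six stated powers to about six decimals:

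| Table | Superiority, HR 0.80 | Non-inferiority, margin 1.3 |
|---|---|---|
| Pooled | 0.99961 | 0.99999 |
| Optum | 0.88467 | 0.96027 |
| MarketScan | 0.98449 | 0.99801 |

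The formula and the database tables are sound. The discrepancy lies in the pooled risk alone.

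**Step 2: where 51.86 comes from.** (58.63 + 45.09) / 2 = 51.86 exactly. Weighting by the final cohorts before matching in Section 5.3 (39,448 and 66,003) would give 50.16, so that does not explain it either.

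**Step 3: the patient-weighted risk.** (6,835 × 58.63 + 15,097 × 45.09) / 21,932 = 1,081,459.78 / 21,932 = 49.31 per 1,000. MarketScan's share is 15,097 / 21,932 = 69%.

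**Step 4: pooled events.** From the database tables, 801.4721 + 1,361.44746 = 2,162.92. The weighted risk gives the same total. The excess is 2,274.79 − 2,162.92 = 111.87 events, and 111.87 / 2,162.92 = 5.2%.

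**Step 5: pooled power with 2,162.92 events, all other inputs as stated.** √(2,162.92 / 4) = 23.254.

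- Superiority at HR 0.80: Φ(23.254 × 0.22314 − 1.96) = Φ(3.229) = 0.9994 (stated 0.9996)
- Non-inferiority at margin 1.3: Φ(23.254 × 0.26236 − 1.96) = Φ(4.141) = 0.99998 (stated 0.99999)

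**Step 6: sensitivity to the hazard ratio.** With |ln 0.81| = 0.21072, superiority power is:

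- Optum: 0.847 with 801.5 events
- MarketScan: 0.973 with 1,361.4 events
- Pooled: 0.998 with the corrected 2,162.9 events

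The Optum and MarketScan event counts do not change. Their lower powers come only from the different hazard ratio.

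**The case against.** The strongest reply is that nothing turns on the error. Correcting the pooled risk alone lowers pooled superiority power by about 0.02 percentage points. The protocol sets no power threshold for the replication and no rule that depends on significance in one database. That stands, and it limits the weight of the point. It does not make the stated count right.

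On the hazard ratio, a reader might infer that all the power figures rest on the wrong effect, or that Optum's power is overstated by about four points (0.885 against 0.847). The documents do not support either reading:

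- Only the three superiority figures use 0.80. The three non-inferiority figures use HR 1 with margin 1.3.
- A hazard ratio of 0.80 is the 20% reduction in Section 1.4, and the appendix trial summary repeats it. Section 1.5 names the estimate to replicate but does not say that power must be computed at that value. The Optum and MarketScan powers are correct for the hazard ratio they openly state.
- Section 10 also requires its parameters, other than the matched numbers, to match Section 8. Changing the hazard ratio in Section 10 alone would break that rule.

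What remains of the hazard-ratio point is ambiguous labelling. The row name does not say whether 0.80 is the trial's design effect or a rounding of its 0.81 result.

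**Conclusion.** The pooled risk and pooled event count in Section 10 are wrong as stated. The table uses 51.86 per 1,000 where the matched numbers give 49.31, and 2,274.8 events where its own components give 2,162.9, an excess of 112 events (5.2%). The error is in both pooled columns.

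The result takes the two database risks in Section 9 and the matched numbers in Section 10 as given, and requires only that the pooled cohort is the two matched cohorts combined, which the arm sizes confirm. No outside figure is needed.

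The consequence is confined to the accuracy of the reported figures. Pooled power stays above 0.998 under every variant examined, including HR 0.81, and no decision to proceed is shown to change. The choice of 0.80 over 0.81 is not shown to be an error; it needs a stated source.

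**What to change.** - In the pooled table, in both columns, replace the risk by 49.31 per 1,000 and the expected events by 2,163.
- Restate pooled power at the stated inputs as 0.9994 (superiority, HR 0.80) and 0.99998 (non-inferiority, margin 1.3).
- Check the pooled calculation in Section 8, since Section 10 carries its other parameters over from there, and correct it too if it holds the same unweighted mean.
- If 0.80 is meant as the Section 1.4 design effect, label it so in the superiority columns. Optionally show power at 0.81 alongside: Optum 0.847, MarketScan 0.973, pooled 0.998.

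This is a spreadsheet correction and a label. It needs no additional patients and no change to the design or analysis, and the restated powers are only slightly less favourable.
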